7.6.3 Other Secondary Efficacy Analyses

7.6.3.1 Pain Freedom at 15, 30, 45, 60 and 90 Minutes

Pain freedom at 15, 30, 45, 60 and 90 minutes is assessed by tabulating the number of mITT subjects that report a pain level of none (responses of 0 on the 4-point Likert scale) at the specified post-dose time point, by treatment group. Subjects with missing data at the specified post-dose time point will be imputed as failures (NC=F). Subjects that use rescue medication prior to the specified post-dose time point will be classified as failures (RM=F).

The proportion of mITT subjects who have a response of pain freedom at the specified post-dose time point will be evaluated using the same methodology described in section [7.6.1.1](#).

7.6.3.2 Freedom from MBS at 15, 30, 45, 60 and 90 Minutes

Freedom from MBS at 15, 30, 45, 60 and 90 minutes post-dose is assessed by tabulating the number of mITT subjects that report an absence of their MBS (reported at migraine onset) at specified post-dose time point, by treatment group. Subjects with missing data at the specified post-dose time point will be imputed as failures (NC=F). Subjects that use rescue medication prior to the specified post-dose time point will be classified as failures (RM=F). Also taking IP prior to reporting the MBS, or failure to report a MBS are events that are imputed as treatment failures (IP=F).

The proportion of mITT subjects who have a response of MBS free at the specified post-dose time point will be evaluated using the same methodology described in section [7.6.1.1](#).

7.6.3.3 Pain Relapse from 2 to 48 Hours

Pain relapse is assessed using the number of mITT subjects that are pain free at 2 hours post-dose as the denominator. The numerator is the number of these subjects that then have a relapse of pain at any severity (response of 1, 2, or 3 on the 4-point Likert scale) within 48 hours after administration of study medication. Subjects with more than 1 time point with missing data or with missing data at the 24, or 48 hour time point are classified as relapse.

If the subject becomes pain-free at 2 hours post dose and records the use of rescue medication, but no pain severity is recorded, it will be assumed that the medication is taken for relapse, and the subject will be counted as having experienced pain relapse.

The proportion of mITT subjects who have a response of pain relapse from 2 to 48 hours will be evaluated using the same methodology described in section [7.6.1.1](#).

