5.4.1 Rescue Medications

After dosing with study medication, all other headache medication is prohibited during the 2 hours post dose. However, a subject who does not experience relief of their migraine headache at the end of two hours after dosing with study medication (and after the two hour assessments have been completed on the eDiary), will be permitted to use the following rescue medication: aspirin, ibuprofen, acetaminophen up to 1000mg/day (this includes Excedrin Migraine) naprosyn (or any other type of non- steroidal anti-inflammatory (NSAID)), antiemetics (e.g., metoclopramide or promethazine), or baclofen. These are the only medications allowed for rescue treatment after 2 hours post dose of study medication.

However, if needed, after 48-hours of administering the one dose of study medication (and before coming in for the End of Treatment Visit) subject may take their prescribed standard of care medications for treatment of migraine (including triptans if not contraindicated, provided all of the assessments have been completed on the eDiary. Similarly, if the migraine is relieved by study medication at 2 hours after dosing but then recurs to a moderate or severe intensity level between two and forty-eight hours, the subject will be permitted to take the same rescue therapy as outlined above. In all circumstances, the subject will always continue to complete his or her eDiary entries through the 48-hour assessment after consuming the study medication. Use of concomitant medication after randomization, including rescue medication, will be recorded by the subject on a paper diary (Concomitant, Adverse Event and Rescue Medication Log) and reported to the site. The site will record medications that were taken within 14 days of dosing with study medication (or until the End of Treatment Visit).

During the 45 days the subject is participating in the study, if the subject has a nonqualifying migraine (mild migraine) or a migraine that they do not treat with study medication, the subject is permitted to use only the following medications: aspirin, ibuprofen, naprosyn (or any other type of non- steroidal anti-inflammatory (NSAID)), antiemetics (e.g., metoclopramide or promethazine), or baclofen.

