9 STATISTICS

9.1 General Procedures

Categorical variables are tabulated with counts and percentages. Continuous variables are summarized with univariate statistics (e.g., n, mean, standard error, median, minimum and maximum).

For the calculation of descriptive statistics of observed data, subjects must have an initial value (e.g. baseline value) to be evaluable for endpoints based on values and changes from the initial value over time.

Tabulations of the following endpoints present the number of unique subjects with an event: protocol deviations; interruptions of study therapy; non-study medications; adverse events; and laboratory abnormalities. Thus, for these endpoints, multiple occurrences of the same event are counted only once per subject.

For the assessments of most endpoints, if a subject uses rescue medication before the endpoint data have been fully collected then the subject will be considered a failure on that endpoint. Full details will be provided in the statistical analysis plan.

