Subjects will record efficacy data in their eDiary. This includes the following: onset time of headache, intensity of the headache prior to and at time of taking study medication. Subject should not dose with study medication until headache reaches moderate to severe intensity. Headache severity will be recorded using a four-point numeric rating scale (no pain, mild pain, moderate pain, severe pain) at the onset of the migraine and after dosing at time points of 15, 30, 45, 60, and 90 minutes and 2, 3, 4, 6, 8, 24 and 48 hours. The presence or absence of associated symptoms (nausea, photophobia, phonophobia) and ratings of functional disability (four-point scale: normal, mildly impaired, severely impaired, requires bedrest) will be recorded at the same time points as the headache severity ratings. Subjects who experience reduction of headache pain to a mild intensity or pain free intensity level will be considered to have achieved pain relief. The subject who does not experience relief of their migraine headache at the end of two hours after dosing with study medication (and after the two hour assessments have been completed on the eDiary) will be permitted to use the following rescue medications: aspirin, ibuprofen, acetaminophen up to 1000mg/day (this includes Excedrin Migraine), naprosyn (or any other type of non-steroidal anti-inflammatory (NSAID)), antiemetics (e.g., metoclopramide or promethazine), or baclofen. These are the only medications allowed for rescue treatment after 2 hours post dose of study medication. If at the end of 48-hours after dosing with study medication (but before the End of Treatment Visit) subjects are in need of migraine relief, they may take their prescribed standard of care medications, including triptans if not contraindicated, provided all of the assessments have been completed on the eDiary. Exclusionary rescue medication such as opioids, ergotamines, butalbital compounds, and muscle relaxants (except baclofen as a rescue medication, see above) are not allowed on this study. Similarly, if the migraine is relieved by study medication at 2 hours after dosing but then recurs to a moderate or severe intensity level between two and forty-eight hours, the subject will be permitted to take the same rescue therapy as outlined above. In all circumstances, the subject will always continue to complete his or her eDiary for up to forty-eight hours after consuming the study medication. During the 45 days the subject is participating in the study, if the subject has a nonqualifying migraine (mild migraine) or a migraine that they do not treat with study medication, the subject is permitted to use only the following medications: aspirin, ibuprofen, naprosyn (or any other type of non-steroidal anti-inflammatory (NSAID)), antiemetics (e.g., metoclopramide or promethazine), or baclofen.

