7.6.2.5 Sustained Pain Freedom from 2 to 48 Hours

Sustained pain freedom is assessed using the number of mITT subjects that experienced no headache pain (response of 0 on Likert scale) at all time points from 2 through 48 hours post-dose. Subjects with missing pain scores at no more than 1 time point, given that they have responses of no pain (response of 0 on Likert scale) at the 2, 24, and 48 hour time points will be considered as successes. Subjects with responses missing at greater than 1 time point; missing data at the 2, 24, or 48 hour time point (NC1=F); or with any pain score greater than 0; or with any rescue medication within 48 hours (RM=F) will be considered as failures.

The proportion of mITT subjects who have a response of sustained pain freedom from 2 to 48 hours will be evaluated using the same methodology described in section [7.6.1.1](#).

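### The rescue sentence for pain relapse (SAP 7.6.3.3) supports two different counts, and read literally it leaves a rescued subject whose later scores are all zero as not relapsed

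*SAP*

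**What the plan says.** SAP 7.6.3.3 takes as its denominator the mITT subjects who are pain-free at 2 hours. Such a subject counts as relapsed by one of three routes:

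- **Score.** "The numerator is the number of these subjects that then have a relapse of pain at any severity (response of 1, 2, or 3"; the window closes 48 hours after dosing.
- **Missing data.** Relapse is also assigned to "Subjects with more than 1 time point with missing data or with missing data at the 24, or 48 hour time point".
- **Rescue.** If the subject "records the use of rescue medication, but no pain severity is recorded, it will be assumed that the medication is taken for relapse".

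Sustained pain freedom from 2 to 48 hours (SAP 7.6.2.5) has matching score and missing-data rules, but its rescue rule carries no condition: subjects "or with any rescue medication within 48 hours (RM=F) will be considered as failures".

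Four other places bear on the point:

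- SAP Section 3 (Study Design) describes the scale: "Headache severity will be recorded using a four-point numeric rating scale (no pain, mild pain, moderate pain, severe pain"). It sets the diary at "time points of 15, 30, 45, 60, and 90 minutes and 2, 3, 4, 6, 8, 24 and 48 hours".
- Protocol 5.4.1 says that if a migraine relieved at 2 hours "recurs to a moderate or severe intensity level between two and forty-eight hours, the subject will be permitted to take the same rescue therapy".
- Protocol 9.1 says, for most endpoints, that "if a subject uses rescue medication before the endpoint data have been fully collected then the subject will be considered a failure on that endpoint", and leaves full details to the SAP.
- SAP 7.4.1 makes all endpoints on or after the rescue date failures when the time of rescue is missing.

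**The concern.** After 8 hours the diary asks for a score only at 24 and 48 hours. A subject can be pain-free from 2 to 8 hours, have a recurrence at 14 hours, take a permitted rescue drug and score 0 at 24 and 48 hours. Every scheduled score is then present and none is above 0. Because 0 is a recorded severity level, the condition in the rescue sentence is not met on its literal wording, and the subject counts as not relapsed.

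That outcome sits badly with Protocol 5.4.1, where the condition for rescue after relief at 2 hours is a recurrence to moderate or severe pain. It also conflicts with 7.6.2.5, where the same subject is a failure because of the rescue. At stake are the reported relapse rates, their difference between arms, and whether relapse and sustained pain freedom tell the same story about the same subjects.

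This is separate from the difference in which scores define relapse (2 or 3 in Protocol 3.2.2 and SAP 4.2.2; 1, 2 or 3 in SAP 7.6.3.3). The rescue problem arises under either definition.

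**Working it through.** The documents give no relapse rate, power or sample size for this endpoint, so there is no plan figure to reproduce. The check is of the classification rule.

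**1. The rules side by side.** Take a subject pain-free at 2 hours. The later scores are at 3, 4, 6, 8, 24 and 48 hours. Each can be 0, 1-3 or missing, and rescue (with a recorded time) can be taken or not. That gives 3^6 x 2 = 1,458 patterns, which fall into six groups:

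| Later scores | Rescue | Sustained pain freedom 2-48 h (7.6.2.5) | Relapse, literal reading | Relapse, if the phrase means no score of 1-3 |
|---|---|---|---|---|
| Any score 1-3 | either | failure | relapse | relapse |
| More than one missing, or 24 h or 48 h missing | either | failure | relapse | relapse |
| One missing at 3, 4, 6 or 8 h, rest 0 | no | success | not relapse | not relapse |
| One missing at 3, 4, 6 or 8 h, rest 0 | yes | failure | relapse | relapse |
| All six 0 | no | success | not relapse | not relapse |
| All six 0 | yes | failure | **not relapse** | relapse |

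On the literal reading, with any missing score enough to trigger the rescue sentence, exactly 1 of the 1,458 patterns disagrees with 7.6.2.5: all six scores 0 plus rescue. If the sentence is triggered only when no later score exists at all, the four rescued patterns with a single missing score also disagree, making 1 + 4 = 5. On the reading in the last column there are none. A count of patterns is not a probability; it only locates the gap.

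**2. Room for the pattern.** The two long unscored intervals are (24 - 8) + (48 - 24) = 16 + 24 = 40 hours, out of 48 - 2 = 46 hours (87%).

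**3. Is relapse an exception within the SAP?** Rescue is a failure without condition for both co-primaries (7.6.1.1, 7.6.1.2), pain relief and normal function (7.6.2.1, 7.6.2.2), both sustained pain freedom endpoints (7.6.2.4, 7.6.2.5), the early pain-freedom and MBS endpoints (7.6.3.1, 7.6.3.2) and every row of SAP Table 1. Apart from rescue use itself (7.6.2.3), relapse is the only binary efficacy endpoint without such a rule.

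**4. Weight of one subject.** Assume 600 evaluable per arm (Protocol Appendix IV) and 2-hour pain-free rates close to the earlier trials in Appendix IV, Table 1 (placebo 10.9-14.2%, rimegepant 19.2-21.2%):

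- Placebo: 600 x 0.11 = 66 to 600 x 0.14 = 84. One subject is 100/66 = 1.5 to 100/84 = 1.2 points.
- Rimegepant: 600 x 0.19 = 114 to 600 x 0.21 = 126. One subject is 100/114 = 0.9 to 100/126 = 0.8 points.

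**5. Effect on the difference, by assumption only.** Let q_P and q_R be the shares of 2-hour pain-free subjects with the uncounted pattern on placebo and rimegepant. On the literal reading the placebo-minus-rimegepant difference is understated by q_P - q_R:

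| Assumed q_P | Assumed q_R | Understatement of the difference |
|---|---|---|
| 2% | 2% | 0 points |
| 5% | 2% | 3 points |
| 10% | 5% | 5 points |
| 2% | 5% | -3 points (overstated) |

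None of these shares comes from the documents.

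**The case against.** The strongest reply is that the literal reading is not the intended one. The preceding paragraph of 7.6.3.3 ties severity to responses of 1, 2 or 3, so a phrase about no recorded severity may mean that no such score was recorded, or that none was recorded at the time of rescue. The missing-score reading also leaves the sentence little to do. Most missing-score cases are already relapses under the missing-data rule, so it adds at most the rescued subject with one missing score at 3, 4, 6 or 8 hours. On the alternative readings the 14-hour example is exactly the case the sentence was written to catch. This argument stands: it rules out saying that the SAP certainly misclassifies the subject. It does not remove the ambiguity, because *no pain* remains a level of the severity scale in SAP Section 3.

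Three stronger inferences are tempting, and the documents do not support them:

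- **That the SAP breaches Protocol 9.1.** That section covers most endpoints and defers to the SAP, so an exception is allowed. What is missing is a reason for it.
- **That every rescue in this group is a relapse.** Protocol 5.4.1 says when rescue is permitted, not why a drug was actually taken, and its list includes antiemetics.
- **That the treatment difference is biased in a known direction.** Step 5 shows none, understatement or overstatement, depending on assumed shares.

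Two further points also stand. SAP 7.4.1 is a partial safeguard, but only when the time of rescue is missing. And no document requires relapse to be the complement of sustained pain freedom; that is a consistency check, not a stated aim.

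**Conclusion.** The point holds as an ambiguity with one identifiable consequence. Read literally, 7.6.3.3 leaves a subject with all later scores 0 and a timed rescue as not relapsed, while 7.6.2.5 calls the same subject a failure. Read the other way, the subject is a relapse. The text supports both counts, and the SAP gives no reason for handling rescue differently here.

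The size cannot be derived from the documents, which give neither a relapse rate nor a rescue rate among 2-hour responders. What can be said, under the assumptions in step 4, is that each such subject moves an arm's relapse rate by about 0.8-1.5 points.

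Pain relapse is an other secondary endpoint outside the Hochberg family, so no co-primary or key secondary conclusion changes. Severity is minor. Confidence is moderate, because the intended reading may already be the desired one.

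**What to change.** Replace the rescue sentence in SAP 7.6.3.3 with: *Subjects pain-free at 2 hours who take any rescue medication after the 2-hour report and within 48 hours are classified as relapse, regardless of recorded pain scores.* State that rescue is defined as in 7.6.2.5.

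With this change the enumeration gives 0 mismatches in 1,458 patterns. Among subjects pain-free at 2 hours, relapse then becomes the exact complement of sustained pain freedom from 2 to 48 hours, provided that subjects who took rescue before the 2-hour report are already failures at 2 hours, as 7.6.1.1 implies.

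The cost is one SAP sentence and one line of programming. SAP 7.6.2.3 already lists the date and time of rescue, so no new data are needed. The downside is that relapse rates may be slightly higher than on the literal reading. Some rescue not taken for headache, such as an antiemetic, would also be counted, as 7.6.2.5 already does. If the sponsor prefers a conditional rule, the SAP should say which scores the condition refers to and why relapse differs from the other endpoints.

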7.6.4 Exploratory Efficacy Analyses

7.6.4.1 Binary Exploratory Endpoints

The binary exploratory endpoints will be evaluated using the same methodology described in section 7.6.1.1. The definitions of the binary exploratory endpoints are listed in the table 1 below.

Table 1 Definitions of the Binary Exploratory Endpoints

| Endpoints | Definition of Success | Missing Data or Rescue Medication Handling |
|---|--|--|
| Pain Relief at 15, 30, 45, 60, and 90 minutes, 3, 4, 6, 8, 24, and 48 hours post-dose | Report a pain level of none or mild (responses of 0 or 1 on the 4-point Likert scale) at specified post-dose time point | NC=F; RM=F |
| Pain freedom at 3, 4, 6, 8, 24, and 48 hours post-dose | Report a pain level of none (responses of 0 on the 4-point Likert scale) at specified post-dose time point | NC=F; RM=F |
| Freedom from MBS at 3, 4, 6, 8, 24, and 48 hours post-dose | Report an absence of their MBS (reported at migraine onset) at specified post-dose time point | NC=F; RM=F; IP=F |
| Function normally at all post-dose timepoints except 2 hours | Subjects who report “abnormal” at baseline and have a response of “normal” at specified post-dose time point | NC=F; RM=F |
| Freedom from phonophobia at all post-dose time points | Subject who have phonophobia present at baseline and have absence of phonophobia at specified post-dose time point | NC=F; RM=F |
| Freedom from photophobia at all post-dose time points | Subject who have photophobia present at baseline and have absence of photophobia at specified post-dose time point | NC=F; RM=F |
| Freedom from nausea at all post-dose time points | Subjects who have nausea present at baseline and have absence of nausea at specified post-dose time point | NC=F; RM=F |
| Sustained pain relief from 2 to 24 hours | Subjects that experience no or mild headache pain (response of 0 or 1 on Likert scale) at all time points from 2 through 24 hours post-dose; Subjects with missing pain scores at 1 or fewer | NC1=F; RM=F |

| Endpoints | Definition of Success | Missing Data or Rescue Medication Handling |
|---|---|--|
| | time points, given that they have responses of no or mild pain (response of 0 or 1 on 4-point Likert scale) at all other time points including the 2 and 24 hour post-dose time points, will be considered as successes. | |
| Sustained pain relief from 2 to 48 hours | Subjects that experience no or mild headache pain (response of 0 or 1 on Likert scale) at all time points from 2 through 48 hours post-dose; Subjects with missing pain scores at 1 or fewer time points, given that they have responses of no or mild pain (response of 0 or 1 on 4-point Likert scale) at all other time points including the 2, 24 and 48 hour post-dose time points, will be considered as successes. | NC1=F; RM=F |
| Freedom from MBS from 2 to 24 hours post-dose | Subjects that experience freedom from their MBS at all time points from 2 through 24 hours post-dose; Subjects with missing MBS data at 1 or fewer time points, given that they have responses of freedom from MBS at all other time points including the 2 and 24 hour post-dose time points will be considered as successes. | NC1=F; RM=F; IP=F |
| Freedom from MBS from 2 to 48 hours post-dose | Subjects that experience freedom from their MBS at all time points from 2 through 48 hours post-dose; Subjects with missing MBS data at 1 or fewer time points, given that they have responses of freedom from MBS at all other time points including the 2, 24, and 48 hour post-dose time points will be considered as successes. | NC1=F; RM=F; IP=F |

| Endpoints | Definition of Success | Missing Data or Rescue Medication Handling |
|--|--|--|
| Function normally from 2 to 24 hours post-dose | Subjects that experience normal functioning on the FDS at all time points from 2 through 24 hours post-dose. Subjects with missing FDS scores at 1 or fewer time points, given that they have responses of normal at all other time points including the 2 and 24 hour post-dose time points will be considered as successes. | NC1=F; RM=F |
| Function normally from 2 to 48 hours post-dose | Subjects that experience normal functioning on the FDS at all time points from 2 through 24 hours post-dose. Subjects with missing FDS scores at 1 or fewer time points, given that they have responses of normal at all other time points including the 2, 24 and 48 hours post-dose time points will be considered as successes. | NC1=F; RM=F |

